**Part A (n = 3-18)**

Abbreviations: D = day; DLT = dose-limiting toxicity; MTD = maximum tolerated dose; n = number of patients; Ph = Phase; Q12H = every 12 hours; Q21D = every 21 days.

**Figure JFCU.8.1. Illustration of study design.**

Part A is a single-arm, dose-escalation study to determine the recommended dose for the expansion cohort (Part B).

**Part A:****Cohort 1**

- Necitumumab, administered I.V. over 60 minutes at an absolute dose of 800 mg on Days 1 and 8, followed by
- Abemaciclib at a dose of 100 mg orally Q12H on Days 1 to 21

**Cohort 2**

- Necitumumab, administered I.V. over 60 minutes at an absolute dose of 800 mg on Days 1 and 8, followed by
- Abemaciclib at a dose of 150 mg Q12H on Days 1 to 21

**Cohort 3**

- Necitumumab, administered I.V. over 60 minutes at an absolute dose of 800 mg on Days 1 and 8, followed by
- Abemaciclib at a dose of 200 mg Q12H on Days 1 to 21

Note: At the time of approval of the JFCU(b) protocol amendment, all patients who are still on the study will be administered necitumumab I.V. infusion over 60 minutes.

A maximum of 18 evaluable patients will be enrolled in Part A. Any patient who is discontinued from the study before completing Cycle 1 will be excluded from the DLT population, unless a DLT was observed. Patients who do not complete Cycle 1 for reason other than DLT will be replaced.

If 1 of 3 patients in each cohort experiences a DLT during Cycle 1, 3 additional patients will be enrolled in that cohort. If 2 of 6 patients experience a DLT in Cohort 1, the study must be discontinued.

If 2 of 6 patients experience a DLT in Cohort 2 or 3, then the dose in Cohort 1 or 2 will be the MTD.

Dose escalation within a cohort will not be permitted. Patients assigned to a cohort dose level will remain at that level throughout the study. However re-escalation will be permitted as specified in Section 9.3.2.2.1.

The individual recommended dose for necitumumab is 800 mg on Days 1 and 8 every 21 days and 200 mg Q12H for abemaciclib. For this reason, further dose escalation beyond Cohort 3 will not be tested.

Patients in whom DLT occurs in Cycle 1 may still continue study treatment according to the criteria for starting the next cycle or dose modification (specified in Section 9.3.2.2.1) if the patients are benefiting from study treatment in the opinion of the investigator.

Necitumumab plus abemaciclib may be continued at the assigned dose level until disease progression, the development of unacceptable toxicity or withdrawal of consent by the patient, or sponsor/investigator decision.

Part B is a single-arm study to evaluate efficacy and safety of necitumumab in combination with abemaciclib in patients with Stage IV squamous or nonsquamous NSCLC (Figure JFCU.8.1). Patients will be treated with necitumumab 800 mg on Days 1 and 8 every 21 days and the dose of abemaciclib identified from Part A of the study Q12H on Days 1 to 21.

Provided there is an acceptable safety profile in Part A of this study, Part B will be initiated, which will include a safety interim analysis after the first 15 evaluable patients have completed 2 cycles of study treatment (or otherwise discontinued study treatment). Patients with squamous and nonsquamous NSCLC who received the recommended abemaciclib dose for Part B in Part A will be taken into account for the safety interim analysis.

The final analysis for all outcomes will be performed approximately 5 months after completing enrollment of the study population.

A treatment cycle will be defined as 21 days. Study therapy, consisting of necitumumab plus abemaciclib will continue until there is a radiographic documentation of PD, toxicity requiring cessation, protocol noncompliance, or withdrawal of consent.

Terms used to describe the periods during the study are defined below:

- **Baseline:** begins when the ICF is signed and ends at the first study treatment (or at discontinuation, if no treatment is given).
- **Study Period:** begins at the first study treatment and ends at study completion. The study period does not include the continued access period.
  - **Study Treatment Period:** begins at the first study treatment and ends when the patient and the investigator agree that the patient will no longer continue study treatment. The date of this agreement is to be reported on the case report form (CRF) as the Date of Discontinuation from study treatment.
  - **Postdiscontinuation Follow-Up:** begins the day after the patient and the investigator agree that the patient will no longer continue study treatment.

*Short-term follow-up* begins the day after the patient and the investigator agree that the patient will no longer continue study treatment and lasts approximately 30 days.

[figure not shown]
*Long-term follow-up* begins the day after short-term follow-up is completed and continues until the patient's death or overall study completion.

- **Continued Access Period:** begins after study completion and ends at the end of trial. During the continued access period, patients on study treatment who continue to experience clinical benefit and no undue risks may continue to receive study treatment until one of the criteria for discontinuation is met. The continued access period includes continued access follow-up.
  - Continued access follow-up: begins the day after the patient and the investigator agree that the patient will no longer continue treatment in the continued access period and lasts approximately 30 days.

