#### 9.3.1. Selection and Timing of Doses

The first treatment will be administered within 7 days of enrollment. Study treatment will be administered as described in Section 9.1.

A cycle is defined as an interval of 21 days.

Administration of necitumumab Day 1 dose will trigger the start of a new cycle. Infusions administered within 3 days before or after the planned infusion time point due to holidays, weekends, bad weather, or other unforeseen circumstances will be permitted and not counted as a protocol deviation. The necitumumab Day 8 dose can be delayed up to 5 days. Beyond that, the Day 8 dose will have to be omitted in order to maintain the 21 day cycle. **A minimum of 7 days' interval between any necitumumab dose must be maintained.**

Abemaciclib will be taken orally every 12 ( $\pm 2$ ) hours on Days 1 through 21 of a 21-day cycle, for a total of 42 doses per cycle. During all cycles, abemaciclib should be taken at approximately the same times each day. If a patient misses or vomits abemaciclib, that dose should be omitted.

In the event of a cycle delay due to logistical reasons (for example, due to patient availability), the patient should continue on abemaciclib treatment. If abemaciclib is interrupted as a result of not having sufficient drug supply, the treatment may be delayed up to 5 days (and not be considered a protocol violation). In exceptional circumstances, a delay  $>5$  days is permitted upon agreement between the investigator and the Lilly CRP.

A patient may continue to receive study treatment until he or she meets 1 or more of the specified reasons for discontinuation (as described in Section 7.3).

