#### 9.3.2. Special Treatment Considerations

##### 9.3.2.1. Dose-Limiting Toxicity (Part A)

A dose-limiting toxicity (DLT) is defined as one of the following AEs, occurring in Cycle 1 if considered to be definitely, probably, or possibly related to necitumumab and abemaciclib. The following list will define DLT:

- Grade 3 or 4 nonhematologic toxicity according to the NCI CTCAE Version 4.0 except for nausea, vomiting, diarrhea, or electrolyte disturbance (see below)
- Grade 3 or 4 nausea, vomiting, or diarrhea that persists more than 2 days despite maximal supportive intervention
- Grade 3 thrombocytopenia with bleeding requiring transfusion
- Grade 4 thrombocytopenia with or without bleeding

- Grade 4 neutropenia that persists more than 5 days
- Grade 3 or 4 neutropenia with fever
- Grade  $\geq 3$  skin toxicity despite best supportive care
- If a total at least 75% of the planned dose for both agents cannot be administered in the first cycle due to toxicity

DLT is defined by sponsor and Principal Investigator.

The following toxicities will not be considered DLTs if they are transient (<7 days) with full supportive therapy:

- Grade 3 arthralgia or myalgia
- Grade 3 asthenia or fatigue
- Grade 3 constipation

The following toxicities will not be considered DLTs:

- Grade 3 injection-site reaction
- Grade 3 elevation of transaminases lasting <7 days
- Grade 3 elevation of serum-bilirubin lasting <7 days
- Transient Grade 3 elevation or decrease of electrolytes
- Grade 3 or 4 hypersensitivity

If a Grade 3 or 4 infusion-related reaction (hypersensitivity) to necitumumab occurs, this event will not be considered a DLT; the patient will not receive any further study therapy and will be replaced in the study by a new patient.

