### **9.6. Treatment Compliance**

Necitumumab will be administered intravenously at the investigational site, under the direction of the investigator. As a result, a patient's compliance with study drug administration is ensured. Patients should attend scheduled clinic visits and must comply with study criteria under their control.

Compliance with abemaciclib will be assessed at Day 1 and Day 8 of each cycle by evaluating patient diaries and counting returned tablets.

Patients who are significantly noncompliant will be discontinued from the study. A patient will be considered significantly noncompliant if he or she misses more than 5 consecutive days of

study medication, or more than 25% of the intended dose of study medication during any cycle (not applicable in case of omission or dose reduction of abemaciclib due to AE). Similarly, a patient will be considered significantly noncompliant if he or she is judged by the investigator to have intentionally or repeatedly taken  $\geq 125\%$  of the planned doses of study treatment in a cycle.

Potential discontinuation of a patient due to study drug noncompliance will be discussed between the investigator and the Lilly CRP before any determination is made to discontinue the patient.

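### Part A sets no minimum Cycle 1 exposure for DLT evaluability, so a patient who misses much of one drug for non-toxicity reasons can count as DLT-free

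*Protocol*

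**What the plan says.** The primary objective of Part A is the number of patients with a DLT in Cycle 1 (Protocol 6.1). The passages that decide who is counted are these.

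- **Exclusion** (Protocol 8.1, after Cohort 3): "Any patient who is discontinued from the study before completing Cycle 1 will be excluded from the DLT population, unless a DLT was observed".
- **Replacement** (same place): "Patients who do not complete Cycle 1 for reason other than DLT will be replaced". Section 9.3.2.1 adds one further replacement rule, for Grade 3 or 4 infusion-related reactions to necitumumab.
- **Cycle** (Protocol 9.3.1): "A cycle is defined as an interval of 21 days".
- **Permitted shortfall in necitumumab** (9.3.1): Day 8 may slip by up to 5 days. "Beyond that, the Day 8 dose will have to be omitted in order to maintain the 21 day cycle".
- **Abemaciclib** (9.3.1): twice daily "for a total of 42 doses per cycle". Missed doses are not made up.
- **The one Cycle 1 dose criterion** (9.3.2.1) is an item in the DLT list: "If a total at least 75% of the planned dose for both agents cannot be administered in the first cycle due to toxicity".
- **Noncompliance** (9.6): missing more than 5 consecutive days, or more than 25% of the intended dose in a cycle, leads to discontinuation from the study after the investigator and the sponsor physician have discussed it. "Compliance with abemaciclib will be assessed at Day 1 and Day 8 of each cycle". Necitumumab compliance is taken as assured because the site gives the infusion.

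SAP 5.2 defines an all-enrolled, a safety and an evaluable population. The last serves efficacy, and none is a DLT population. SAP 5.7.3 lists the Part A patients who had a DLT and gives no denominator.

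**The concern.** A DLT count describes the tolerability of a stated combination only if the counted patients received something close to it. Here the test is whether the patient reached the end of a calendar interval. The 75% criterion does not fill the gap: it applies only when toxicity caused the shortfall, and then it makes the patient a DLT. A shortfall of the same size with another cause has no stated effect on the count.

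If lower exposure means lower DLT risk, the error runs one way, towards passing the dose level. Cohorts have 3 to 6 patients, so one such patient can change a decision, and the dose chosen in Part A goes forward to Part B.

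**Working it through.** **Step 1. The plan's own figure.** Three cohorts of at most 6 patients give 3 × 6 = 18, the stated Part A maximum. The documents give no escalation probabilities.

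**Step 2. How much can be missed.**

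- Necitumumab: one of two planned infusions omitted = 1/2 = 50% of the Cycle 1 amount.
- Abemaciclib: 2 × 21 = 42 planned doses. Five days missed = 10/42 = 23.8%, so 76.2% is taken. Six days missed = 12/42 = 28.6%.
- The 25% limit in 9.6 is crossed at 11 missed doses (11/42 = 26.2%).

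**Step 3. When the shortfall is seen.** After the Day 8 check, the next abemaciclib compliance check is Cycle 2 Day 1. A patient who misses 11 or more doses, mostly after Day 8, is therefore first identified once Cycle 1 is complete, when the exclusion in 8.1 no longer applies. An omitted Day 8 infusion is known earlier, by about Day 13 (8 + 5), but 9.3.1 expressly permits the omission.

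**Step 4. Effect on a cohort decision.** From the expansion and stopping rules in 8.1, a dose level is taken to pass with 0/3 DLTs, or with 1/3 followed by 0/3. This is inferred, since the design figure is not shown.

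P(pass) = P(0 of first 3) + P(1 of first 3) × P(0 of next 3)

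Assume a true DLT risk of 1/3 at full exposure, and at most one under-exposed patient, among the first three. The next three are fully exposed, so P(0 of next 3) = (2/3)³ = 0.296.

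| First three patients | P(0/3) | P(1/3) | P(pass) |
|---|---|---|---|
| All fully exposed | 0.296 | 0.444 | 0.296 + 0.444 × 0.296 = 0.428 |
| One at half the risk (1/6) | 0.370 | 0.444 | 0.370 + 0.444 × 0.296 = 0.502 |
| One at no risk | 0.444 | 0.444 | 0.444 + 0.444 × 0.296 = 0.576 |

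**Step 5. Range over the assumed risk**, again with one under-exposed patient among the first three:

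| Assumed DLT risk | All fully exposed | One under-exposed (half risk to no risk) |
|---|---|---|
| 0.2 | 0.709 | 0.756–0.804 |
| 0.3 | 0.494 | 0.564–0.634 |
| 0.4 | 0.309 | 0.386–0.464 |
| 0.5 | 0.172 | 0.242–0.312 |

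**Step 6. Average effect if under-exposure is rare.** Suppose, for illustration, that each of the first three patients has a 5% chance of being under-exposed. The chance of at least one is 1 − 0.95³ = 0.143. The average risk per patient becomes (1/3) × (1 − 0.05 × 0.5) = 0.325 at half risk, or (1/3) × 0.95 = 0.317 at no risk. P(pass) then averages 0.439 to 0.451, which is 1 to 2 percentage points above 0.428. If the three expansion patients carry the same 5% chance, it averages 0.444 to 0.461, or about 2 to 3 points above.

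**The case against.** The strongest reply is that other rules already deal with most of these patients. Four parts of it have force.

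- **Section 9.6.** A non-toxicity omission of the Day 8 infusion is 50% of that drug, above the 25% limit, and is known within Cycle 1. The patient could be discontinued, excluded and replaced in time, and so could a patient with an early abemaciclib loss. This narrows the gap without closing it: discontinuation is not automatic, 9.3.1 allows the same omission, 9.6 is silent on the DLT population, and late abemaciclib losses surface too late.
- **Supply gaps.** A reader might cite this sentence in 9.3.1: "If abemaciclib is interrupted as a result of not having sufficient drug supply, the treatment may be delayed up to 5 days". It is not an example. It follows a sentence about late cycles, so it may not concern Cycle 1 at all. Even within Cycle 1 it leaves 76.2% of doses taken, which a 75% threshold would accept. Longer gaps need exceptional circumstances and the sponsor physician's agreement.
- **Vomited doses.** A reader might add these. Treatment-related vomiting that causes a shortfall may already fall under the toxicity criterion in 9.3.2.1.
- **Completing Cycle 1 is not itself defined.** Reading it as 21 calendar days follows from the definition of a cycle, but a site could read it as completing treatment. That ambiguity is a further reason to write the rule down.

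The consequences are also bounded. Escalation ends at Cohort 3, Part B is described as dose confirmation, and a safety interim follows the first 15 evaluable Part B patients and includes Part A patients treated at the chosen dose. These checks come after the dose has been chosen, so they limit the harm without correcting the Part A count.

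**Conclusion.** The point holds in a limited form. As written, the rules let an event-free patient count as DLT-free after losing half of Cycle 1 necitumumab for non-toxicity reasons, or more than 25% of abemaciclib mostly late in the cycle. The bias is towards escalation, provided that lower exposure lowers DLT risk.

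The size is conditional. With a true DLT risk of 1/3 and one under-exposed patient among the first three, the pass probability goes from 43% to 50–58%. For risks of 0.3 to 0.5 the increase is about 7 to 16 percentage points. The DLT risk, the presence of an under-exposed patient and that patient's reduced risk are all assumptions. If under-exposure is uncommon, the average shift is a few points at most.

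A reader might infer that Part A has no safeguard at all, or that the dose carried into Part B is likely to be too high. The documents support neither. Sections 9.3.2.1 and 9.6 give partial protection, and nothing in the documents shows how often such shortfalls occur.

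**What to change.** In Protocol 8.1, and as a population in SAP 5.2, define DLT-evaluable patients as those who had a Cycle 1 DLT, or who completed Cycle 1 having received a pre-specified minimum share of the planned Cycle 1 amount of each drug. State what completing Cycle 1 means. Exclude from the DLT count, and replace, DLT-free patients who fall short for reasons other than toxicity. Report DLT counts by cohort on this set, in addition to the listing in SAP 5.7.3.

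The sponsor must set the threshold. The 75% already in 9.3.2.1 is a natural candidate, but there it defines a toxicity DLT and not evaluability. It needs to be reconciled with 9.3.2.1, with the permitted Day 8 omission in 9.3.1 and with the 25% rule in 9.6. With two planned infusions, 75% of necitumumab in effect requires both.

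The text change is small, and the dose data are already collected for the exposure summaries in SAP 5.7.1. The downside is an occasional extra replacement patient in Part A, and a judgement on whether each shortfall was due to toxicity. If Part A enrolment is already complete, only the SAP population and the by-cohort report apply.

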### **8.1.1. Study Completion and End of Trial**

This study will be considered complete (that is, the scientific evaluation will be complete [study completion]) approximately 5 months after the last patient in the Part B of the study has been enrolled. Investigators will continue to follow the study schedule for all patients until notified by Lilly that study completion has occurred. "End of trial" refers to the date of the last visit or last scheduled procedure for the last patient.

The end of trial occurs after study completion and after the last patient has discontinued study treatment and completed any applicable continued access follow-up (see [Figure JFCU.8.2](#)).

**Figure JFCU.8.2. Study period and continued access diagram.**

### 8.1.2. Continued Access Period

The continued access period will apply to this study only if at least 1 patient is still on study treatment when study completion occurs. Patients receiving study treatment and experiencing ongoing clinical benefit and no undue risks may continue to receive study treatment in the continued access period until one of the criteria for discontinuation is met (Section 7.3). Lilly will notify investigators when the continued access period begins.

Patients who are in short-term follow-up when the continued access period begins will continue in short-term follow-up until the 30-day short-term follow-up visit is completed. Long-term follow-up does not apply.

Patients who are in long-term follow-up when the continued access period begins will be discontinued from long-term follow-up.

During the continued access period, all AEs, SAEs, and study drug exposure will be reported on the CRF. Serious adverse events will also be reported to Lilly Global Patient Safety (see Section 10.2.1.1). In the event that an SAE occurs, Lilly may request additional information (such as local laboratory results, concomitant medications, and hospitalizations) in order to

evaluate the reported SAE. Blood samples for PK and immunogenicity analysis will be collected in the event of an infusion-related reaction and during the continued access follow-up.

During the continued access period, the sponsor will collect only the data shown in [Attachment 1](#). It is recommended that routine monitoring, using an assessment schedule similar to that outlined in [Attachment 1](#) (including radiographic evaluation of disease), be continued as necessary to confirm patient eligibility to continue on treatment. However, the results of all these assessments may not be routinely collected by the sponsor, and all nonmandatory assessments (that is, all assessments not explicitly described in [Attachment 1](#)) may be performed locally rather than centrally.

## 8.2. Discussion of Design and Control

In this single-arm, Phase 1b study with an expansion cohort, the selected dose of necitumumab of 800 mg on Days 1 and 8 every 21 days is aligned with the MTD and the dosing schedule in the Phase 3 development program for necitumumab. The starting dose of abemaciclib will be at dose level -2 of the MTD (100 mg Q12H). This is aligned with the minimal dose applied in the dose adjustment schedule from clinical trials.

Patients with Stage IV NSCLC who have received no more than 2 lines of chemotherapy, of which at least one must be platinum-based, for advanced or metastatic disease will receive a combination of necitumumab and abemaciclib. Prior treatment with EGFR-TKI, VEGF/VEGFR-targeting agents, and ALK inhibitors is permitted.

In Part B, approximately 50 patients will be enrolled with an even split between squamous and nonsquamous histology to enable a homogenous population in the study.

Provided there is an acceptable safety profile in Part A of this study, Part B will be initiated, which will include a safety interim analysis after the first 15 evaluable patients have completed 2 cycles of study treatment (or otherwise discontinued study treatment). Patients with squamous and nonsquamous NSCLC who received the recommended abemaciclib dose for Part B in Part A will be taken into account for the safety interim analysis.

Based on the single-arm nature of the study, the outcome will be hypothesis generating only, allowing for future consolidation of this regimen depending on the outcome.

## 9. Treatment

### 9.1. Treatments Administered

The following treatments will be administered in this study (Table JFCU.9.1):

In Part A, patients will receive oral abemaciclib 100 mg, 150 mg or 200 mg Q12H in combination with necitumumab 800 mg as an absolute dose on Day 1 and Day 8 every 21 days.

In Part B, the abemaciclib dose identified from Part A will be given Q12H in combination with necitumumab 800 mg as an absolute dose Day 1 and Day 8 every 21 days.

Necitumumab will be administered first followed by abemaciclib. Abemaciclib should be administered within 10 minutes of start of necitumumab infusion.

